objective outcomes: cancer recurrence and complications; and subjective outcomes: health related quality of life, psychological well-being, satisfaction with decision and satisfaction with care. **Outcomes Assessment:** As part of Specific Aim 2, following instruments will be used to measure preferences for participation in treatment decision, decision conflict and physician trust for both intervention group and the usual care control group at baseline, immediately after treatment decision, but prior to initiation of treatment. **Control Preferences Scale (CPS):** The CPS assesses the role that patients want to play and perceive playing in treatment decisions [259]. It consists of five sort-cards to assess different roles in decision making, ranging from a fully active to a fully passive role. This survey will be administered at baseline only. **Decision Conflict Scale (DCS):** The DCS is based on a conceptual framework of decision conflict, which is a state of uncertainty about which course of action to take. This scale is well studied in cancer area and has good psychometric properties [260]. We will administer this survey at baseline (before treatment). **Patient Trust-Wake Forest Physician Trust Scale:** This 10-item instrument is

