
common pattern of the Gleason grade. Gleason score ranges from 2 -10 classified as low (2-4), intermediate (5-7) or high-grade (8-10). Elixhauser comorbidity index: The Elixhauser comorbidity index is a medical record-based metric designed to predict death in longitudinal studies, with an integer score representing increasing burden of illness [278]. We will use diagnostic information from inpatient encounters in 180 days prior to the month of PCa diagnosis to adjust for comorbidity, following the method of Elixhauser et al. [167,168,] and will obtain comorbidity scores using PICARD and VA inpatient and outpatient databases. Demographic variables: We will gather baseline data on patient age, income, education, health insurance, occupation, marital status, smoking status, height, weight and family history of PCa as possible covariates in our analyses.

Secondary outcome variable(s)

None

Background

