
among treatment features will be calculated in patient-specific utilities or part-worths associated with the attribute levels in the study. For other outcomes, participants will receive the following surveys via mail within 1-2 weeks after enrollment and prior to treatment initiation: SF-36, EPIC, AUA-SI, regret scale, CES-D, MAX-PC, SWD, PSQ-18, CPS, DCS and trust scale. Demographics, health and family history, clinical covariates and cancer progression data will be collected at 3, 6, 12 and 24 month follow-up. Histological tumor grade Gleason score and PSA and annual Elixhauser comorbidity score [257-258] will be obtained from the Pennsylvania Integrated Clinical and Research Database (PICARD), a UPHS, Fox-Chase Cancer Center electronic database, and PVAMC administrative and patient HER database. Retention and survey administration: During enrollment, importance of active participation will be emphasized. All participants will complete self-administered surveys at baseline within 1-2 weeks after enrollment (prior to treatment initiation) and again 3,6,12 and 24 months post-enrollment (see Appendix for copies of instruments, consent and medical chart review form). Non-respondents will be contacted via telephone after 10 days. In case of non-response due to death, cause of death will be noted and the physician investigators will determine cause of death (PCa or non-PCa related). The PCa conjoint analysis task, DCS, CPS and trust scale will be administered at baseline only, immediately after diagnosis of PCa and before treatment decision. D.2.4 Outcomes Assessment: D.2.4.1 As part of Specific Aim 2, following instruments will be used to measure preferences for participation in treatment decision, decision conflict and physician trust for both intervention group and the usual care control group at baseline, immediately after treatment decision, but prior to initiation of treatment. D.2.4.1.1 Control Preferences Scale (CPS): The CPS assesses the role that patients want to play and perceive playing in treatment decisions [259]. It consists of five sort-cards to assess different roles in decision making, ranging from a fully active to a fully passive role. This survey will be administered at baseline only. D.2.4.1.2 Decision Conflict Scale (DCS): The DCS is based on a conceptual framework of decision conflict, which is a state of uncertainty about which course of action to take. This scale is well studied in cancer area and has good psychometric properties [260]. We will administer this survey at baseline (before treatment). D.2.4.1.3 Patient Trust-Wake Forest Physician Trust Scale: This 10-item instrument is based on a multi-dimensional conceptual model of trust and measures trust in physicians and other health care providers [128-130]. Compared with previous scales, it showed improved internal consistency and variability [129, 131-132, 261]. Trust is measured by the sum of the 10 item scores, ranging from 10 to 50, with a higher score indicating higher trust [129, 131-132, 261]. D.2.4.2 As part of Specific Aim 3, the following outcomes will be measured for both intervention group and the usual care control group after initiation of treatment. D.2.4.2.1 Treatment choice: We will obtain data on primary and secondary treatments received, such as active surveillance, RP, RALP, EBRT, BT or PT via self report and verified from medical chart review. . D.2.4.2.2 Satisfaction with Decision (SWD): The SWD scale measures satisfaction with healthcare decisions. It was developed in the context of postmenopausal hormone-replacement therapy decisions. The six-item scale has excellent reliability (Cronbachs alpha = 0.88) [262]. D.2.4.2.3 Regret scale: Regret represents the unsettling feeling of having made a poor choice of treatment, persistent doubt, and a wish to change one's mind. The Regret scale is defined by three items that assess (1) the mans wish that he could change his mind about the kind of treatment he has received, (2) his feeling that he would be better if he had chosen the other treatment, and (3) whether he is bothered by the fact that other men received very different treatments for their PCa [33]. This scale exhibited good psychometric properties and has been extensively studied [33, 174, 263-265]. D.2.4.3 Following objective and subjective outcome measures will be assessed at baseline and at each post-treatment follow-up period (3,6,12 and 24 months) for intervention group and usual care control group. D.2.4.3.1 Biochemical recurrence: We will define progression of PCa as a change in PCa stage to an advanced stage or PSADT, post treatment [11, 44-45, 55, 160, 203]. We will obtain PSA data at baseline, prior to treatment, and post treatment at three months interval for 18 months. A PSA value of greater than 0.2 ng/ml indicates disease recurrence for surgery patients. For radiation therapy patients, we will adopt the Houston /Phoenix definition of the current PSA nadir + 2 ng/mL, with date of failure determined at call as the biochemical recurrence after radiation therapy [11, 44-45, 55, 160, 203]. Any treatment within six-month of diagnosis will be considered as adjuvant (review by investigators Drs. [name], [name], and [name]). D.2.4.3.2 Medical complications: We will identify complications that occur during either index or subsequent PRINCIPAL INVESTIGATOR (LAST, FIRST, MIDDLE): [name] PCORI Research Plan: Research Strategy 11 hospital admissions within 30 days of treatment [266]. Alibhai, et al. (2005), has grouped complications after RP into seven mutually exclusive categories: cardiac; respiratory; genitourinary; wound or bleeding; vascular; miscellaneous medical; and miscellaneous surgical [266]. Similarly, a list of complications for each treatment type will be developed by literature review and the physician investigators and consultants. D.2.4.3.3 Generic HRQoL- Medical Outcome Study Short Form: HRQoL data will be obtained using the Medical Outcome Study Short Form (SF-36) a multi-

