
item scale that assesses eight health domains. This instrument can be self-administered or administered by a trained interviewer, either in person or by telephone. It has been tested extensively for reliability ($r=0.80 - 0.93$) and validity (Cronbachs $=0.92$). Scores on each sub-scale range from 0 to 100, with higher scores indicating better HRQoL [267-271].

D.2.4.3.4 Prostate Cancer HRQoL- Expanded Prostate Cancer Index (EPIC): The EPIC was developed for comprehensive assessment of HRQoL in men with PCa. It is a 50-item expanded edition of the 20-item UCLA Prostate Cancer Index (PCI) and complements other instruments by measuring a broad spectrum of urinary, bowel, sexual and hormonal symptoms. It has good psychometric properties: test-retest reliability and internal consistency are high for EPIC and for most of the subscales [189, 272-273]; construct validity was established using SF-36 as a generic core measure and a cancer-related HRQoL instrument, the Cancer Rehabilitation System-Short Form [189, 272-273]; and is easy to understand and complete [192].

D.2.4.3.5 American Urological Association Symptom Index (AUA-SI): The AUA-SI, a clinically sensible, reliable, valid and responsive index widely used for clinical and research purposes [274], has good internal consistency (Cronbachs $=0.86$), excellent test-retest reliability ($r=0.92$) and sensitivity to change with preoperative scores decreasing from a mean of 17.6 to 7.1 by four weeks after prostatectomy ($p<0.001$).

D.2.4.3.6 Patient Satisfaction Questionnaire (PSQ-18): This 18-item survey [a shorter version of the original Patients Satisfaction Questionnaire [275], assesses global satisfaction with medical care and satisfaction with six aspects of care: technical quality; interpersonal manner; communication; financial aspects of care; time spent with doctor; and accessibility of care. It has demonstrated good internal consistency (Cronbachs $=0.86$) and excellent test-retest reliability ($r=0.92$).

D.2.4.3.7. Memorial Anxiety Scale for Prostate Cancer (MAX-PC): The 18-item MAX-PC identifies three aspects of PCa-related anxiety. It has high internal consistency and concurrent and discriminant validity[276].

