size based on the observed differences in outcomes such as HRQoL (SF-36 and prostate cancer index, PCI) and cost of PCa care across groups. The primary outcome is HRQoL as measured by the SF-36 and PCI sub-scales. A change of 5 to 9 points on PCI is clinically meaningful [272]. Similarly, a difference of 7 points or more on the SF subscales is considered clinically meaningful [272, 275, 301]. Based on our prior research and that of Litwin et al [253, 272], the standard deviations for the PCI and SF-36 scales in samples of men with PCa mostly range from 8 to 14; hence standardized differences (SDs) of $7/14=0.5$ to $7/8=0.87$ will be clinically relevant. The power calculations for Aims 2-4 assume availability of 720 participants who are eligible for randomization into one of the two intervention groups. We assume a conservative intra-class correlation of 0.3 and 4 follow-up measures per subject. The sample size is adjusted to accommodate a 10% missing or dropout rate by 24 months based on rates over a similar period of time in previous studies [272, 275, 301]. We assume 80% power and two-sided level of significance of $\alpha = 0.05$. We have 80% power to detect a 1.2 point difference in PCI or SF-36 sub-scale. Within treatment type, the sample size is reduced to 60 per intervention arm. We have 80% power to detect a 3.0 point difference in sub-scale with 60 patients in each arm. Thus, we will have adequate power to detect differences between treatment groups [302]. Power for identifying utility based profiles and outcomes: We analyzed the levels of power for differences in outcomes between profiles defined by latent classes of attributes-specific utilities with a conservative allocation of subjects to each profile (25 in one vs. 10 in other profile) and less conservative allocation (35 in one profile vs. 35 in other profile) using a logistic model based comparison for a binary outcome (e.g. recovery of baseline HRQoL) with a 2-sided alpha of .0125 (Holms adjustment profiles). In the first allocation, the group difference of 0.56 yields 80% power; for the second allocation an effect size of 0.42 corresponds to power of 90. Thus, with our anticipated effect size of 0.51, we will have adequate power with $n=60$ in each group. (Adjusting for patient characteristics may reduce the effect sizes of the differences between profiles.)

Key inclusion criteria

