
The following documents are currently attached to this item:

There are no documents attached for this item.

Analysis Plan

Analytic Methods General: The statistical analysis will proceed in three stages: First, we will check the data quality and carry out descriptive analyses of demographics and key outcome variables. Next, we will assess preferences using conjoint analysis and inferential analysis. For continuous outcome variables, we will check for homogeneity of errors using spread-vs.-level plots and will consider transforming variables that either are highly skewed or have variance that depends strongly on the mean. We will use methods based on general linear model (univariate and repeated-measures ANOVA, mixed models) to analyze uncensored continuous outcomes, such as generic and prostate-specific HRQoL, psychological wellbeing and satisfaction with care. For potentially censored outcome variables such as time to PSA recurrence, we will use Kaplan-Meier curves and Cox proportional hazard models. Poisson regression (zero-inflated) will be used for count data. We will use Bonferroni correction for multiple testing. We will use propensity-score and instrumental variable approach to minimize observed and unobserved bias within groups (i.e. intervention group and usual care control group). **Missing Data:** We will attempt to prevent missing data by ensuring that data collection is as complete as possible. Should there be substantial missing data, however, we will employ analysis and imputation methods to reduce bias and increase efficiency [279-282]. Based on the proportion of missing data, we will use complete-case analysis, or explore available techniques, such as standardized score imputation, simple means imputation, maximum likelihood model-based imputation, data augmentation, etc. [281]. When data are evidently non-missing at random, we will conduct explicit non-ignorable modeling and sensitivity analysis [278]. **Propensity score matching:** In observational studies, comparisons between treatment groups that do not adjust for factors associated with treatment choice may be biased. Propensity score technique offers a highly practical approach to address such bias [283]. Here, the probability of each participant being in the treatment arm (i.e., the propensity score), is estimated. Participants are sorted by their propensity scores; the sample is divided into strata based on estimated scores, the treatment effect within each stratum estimated and overall estimate computed by aggregating across strata in a weighted analysis. When the model for predicting treatment status includes all relevant covariates, within strata treatment groups will be balanced on all predictors and the overall comparison of treatment arms will have substantially lower bias. We will use a model relating PCa treatment (RP, RALP, EBRT, PT, BT or AS) to baseline factors [283-284]. To study the extent to which treatment groups are now matched, we will compare t-statistics for these covariates before and after adjusting for propensity score. This will be done separately for intervention group and usual care controls. **Instrumental variable analysis:** Another limitation of observational research is the strong potential for confounding bias, due to differences in comparison groups that are not reflected in the data (i.e., unobserved bias). The instrumental variable (IV) approach is useful in reducing this bias. This technique uses one or more observable factors that influence outcome only indirectly (the IV). This allows one to mimic randomization with different likelihoods of receiving a particular treatment [227, 285-291]. Physicians play an important role in patients treatment choice- a majority of the PCa patients report that their physicians recommendation was the most important factor in their treatment choice [11-12, 37-46, 51, 55-56, 60-64]. We will use specialty of the first physician (urologist, urologic oncologist, oncologist, radiation oncologist) who the patient saw during PCa diagnosis as an IV. We will explore other potential IVs, such as absolute distance between patients residence to the hospital where they will receive care (Hospital of University of Pennsylvania, Presbyterian Medical Center, PVAMC, Pennsylvania Hospital, or Fox-Chase Cancer Center). Validity of the IV(s) is assessed as following. First, we will use Pearsons correlation coefficient to examine the correlation between IV, primary exposure (treatment) and outcomes. We will then perform a partial F-test using a linear regression where treatment group is regressed on physician specialty along with patient attributes. For a valid IV, test statistic should be very high (e.g., physician specialty will strongly predict treatment after adjusting for covariates). Next, we will perform a partial F-test using a linear probability model in which HRQoL outcomes are regressed on specialty and patient demographic and clinical variables. For an IV to be valid, this test statistic should be very low. Finally, we will compare observable attributes across patient groups cared for by different physician specialty (initial). For the IV be valid, these groups should have comparable observable attributes. **Phase 1 Focus group analysis-development of conjoint task instrument:** The goal of focus groups is to identify attributes of PCa treatment that are most salient to localized PCa patients. This process includes following steps: (1) identifying and defining attributes; (2) assigning attribute levels; and (3) creating scenarios and choice sets. Attributes will be defined based on input from patient focus groups, literature, our prior research, and prior physician focus group. Once an attribute and its extreme values are defined, we will assign them appropriate levels. A large number of possible combinations of attributes and levels will preclude

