patients in decision (measured using CPS) using multi-nominal regression model to adjust for observed covariates. Then we will examine if these associations vary across intervention and usual care control groups. We then will repeat the model with other independent variables (decision conflict and trust). Next, we will test the association denoted by path c (direct effect of DCS, CPS, and trust on outcomes). For continuous outcomes (HRQoL, AUA-SI, MAX-PC, CES-D, SWD, and PSQ-18), we will compute area under the curve (AUC) for each measure for each patient. We will analyze AUC summaries with univariate linear models. In our main analysis we will analyze the series of functional status measures using linear mixed models that predict the outcome from time, independent variables and their interaction. We will repeat the analyses described for path c, this time by including treatment received in the models. We will test if the observed effects of DCS, CPS or trust on outcomes will be weaker after controlling for treatment. These analyses will be performed within and between groups (intervention and usual care controls). Specific Aim 3: Hypothesis: Prostate cancer patients in the intervention group undergoing conjoint analysis-value clarification exhibit improved treatment choice, satisfaction with decision, lower regrets, and improved objective and subjective outcomes. Analysis for Specific Aim 3 uses intent-to-treat approach: all randomized participants will be included regardless of whether they drop out of the intervention or study. Analysis will involve comparison of the primary outcomes between intervention and usual care control groups. Improved treatment choice is operationalized as the likelihood of low-risk PCa patients receiving active surveillance than active treatment, and will be compared between intervention and usual care control group. To allow for different trajectories of the outcome measures and to afford flexibility in making contrasts within participants over time and across participants, while simultaneously controlling for potential confounders, we propose the participant-specific or mixed effects linear model, in which the mean outcome depends on fixed covariates and random effects. The primary fixed effects will be indicators for intervention group and hospital. We will also stratify the analysis by type of treatment. The random effects represent the unobserved factors that lead to variation of the individual participants outcome. Random intercepts for each participant permit modeling of natural variation across participants at baseline. In addition, random slopes or random effects for the trajectory of each participant over time, allow for variation of each participant about a mean, overall trajectory across all participants. Although less robust to model misspecification, the mixed effects paradigm offers special flexibility in longitudinal data when exposures vary over time and when dropout and missed visits lead to unbalanced groups. The target of inference is the participant-specific response to treatment over time. At each time point of interest, we will estimate from the fitted model the difference from baseline in outcome for the treatment and control groups and test the difference between these differences. Both univariate and multivariate results will be reported in terms of Wald test, point estimates, and 95% confidence intervals. Specific Aim 4: Hypothesis 4: Prostate cancer patients whose treatment is more concordant with their values markers will experience improved subjective and objective outcomes. This specific aim s for intervention group only. We will analyze the association of the concordance between stated individual preferences and actual treatment received with objective (PCa recurrence and complications), subjective (HRQoL, psychological wellbeing, SWD, and satisfaction with care) outcomes, across treatment groups, adjusting for covariates. Association between the value markers (profiles) and measures of outcomes and personal and clinical characteristics: The value markers will be studied for their relationship with socio-demographic and clinical characteristics. We will also assess the association of value markers with outcomes. We will perform logistic regression with outcomes as the dependent variable and dummy variables for the utility-based profiles obtained earlier as independent variables. We will perform this evaluation with and without adjusting for patient attributes in the logistic model. For each case (adjusting and not adjusting for patient attributes), the evaluation of association between these profiles and outcomes will be based on a likelihood ratio test of the set of odds ratios corresponding to the dummy variables of the profiles. Additionally, we will perform a sequence of pair wise tests of comparisons of the profiles in terms of the proportion of type of treatment received based on the Holms multiple comparisons approach. This procedure is hierarchical in that it will identify the utility-based profile at the start of the process before making other comparisons, thus protecting the Type I error from additional comparisons. Specifically, Holms approach tests each pair-wise comparison in ascending order of p-values. Successively larger p-values have less rigorous alpha. The sequential Holm tests terminate after the first non-significant comparison so no subsequent comparison is significance. Concordance and its assessment: Understanding and respect for the patients preference and values is the main aspect of concordance [69, 73]. Thus a first step in concordance involves the physician extracting and understanding the patients view, followed by an agreement between the physician and patient regarding a management plan that integrates their views. There exist many definitions of concordance. For the purpose of this study, we operationalized concordance as agreement between a patients value markers and the attributes (or characteristics) of the treatment that

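### The plan gives two different primary outcomes, and its between-arm detectable differences of 1.2 and 3.0 points hold only without the planned Bonferroni correction, at the lowest SD, and for a four-visit average

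*Combined protocol and SAP*

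**What the plan says.** - **Primary outcome variable(s) field:** "objective outcomes: cancer recurrence and complications; and subjective outcomes: health related quality of life, psychological well-being, satisfaction with decision and satisfaction with care". That is six families. The Secondary outcome variable(s) field that follows reads None.
- **Accrual, sample-size text:** "The primary outcome is HRQoL as measured by the SF-36 and PCI sub-scales". Power is set at 80% with two-sided alpha 0.05. The detectable difference on a sub-scale is given as 1.2 points for the whole trial and 3.0 points with 60 per arm within a treatment type.
- **Analysis Plan, Specific Aim 3 (between-arm, intent-to-treat):** "Analysis will involve comparison of the primary outcomes between intervention and usual care control groups". The outcomes are not named there. The arms are compared on change from baseline at each time point of interest.
- **Analysis Plan, general methods:** "We will use Bonferroni correction for multiple testing". Neither the family nor the number of tests is stated.
- **D.2.3 and Procedures, survey list:** "SF-36, EPIC, AUA-SI, regret scale, CES-D, MAX-PC, SWD, PSQ-18, CPS, DCS and trust scale". EPIC is administered; PCI is not on the list. D.2.4.3.4 describes EPIC as the expanded edition of the PCI.

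**The concern.** A reader cannot tell which result would make this trial positive. Under the outcomes field, all six families are primary and nothing is secondary. Under the sample-size text, only quality of life is. Because Aim 3 refers to the primary outcomes without listing them, it carries the conflict into the main analysis. The family over which Bonferroni applies could then be settled after the data are seen.

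The power statement does not describe the planned analysis either. It takes one sub-scale at an uncorrected alpha, while the plan promises a correction. It averages the follow-ups, while Aim 3 tests each time point. For recurrence, complications, psychological well-being and the two satisfaction outcomes the documents give no between-arm power and no inputs from which to compute it.

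**Working it through.** **Inputs (Accrual unless noted).** 360 per arm overall and 60 per arm within treatment type; 10% dropout, leaving 324 and 54; SD 8 to 14; intra-class correlation 0.3; four follow-up measures; two-sided alpha 0.05; power 80%. Thresholds for a meaningful difference: 5 to 9 points (PCI) and 7 points or more (SF-36 sub-scales).

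**Formula.** Detectable difference = (z for alpha + z for power) × SD × c × √(2/n). For the mean of four visits, c = √((1 + 3 × 0.3)/4) = √0.475 = 0.689. For one visit, c = 1.

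**Reproducing the plan's figures** (alpha 0.05, so 1.960 + 0.842 = 2.802; SD 8; four-visit mean):
- Overall: 2.802 × 8 × 0.689 × √(2/324) = 1.21 (stated 1.2).
- Within type: 2.802 × 8 × 0.689 × √(2/54) = 2.97 (stated 3.0).

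Both match. At SD 14 the same formula gives 2.12 and 5.20, so the stated values sit at the favourable end of the plan's own SD range.

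**Applying the planned correction.** The number of tests k is not stated. As an assumption, take k = 12: eight SF-36 domains plus the four EPIC symptom areas (urinary, bowel, sexual, hormonal). Then alpha = 0.05/12 = 0.00417, z = 2.865, and 2.865 + 0.842 = 3.707.

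Detectable differences in points, SD 8 to 14:

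| | Four-visit mean, alpha 0.05 | Four-visit mean, k = 12 | One visit, alpha 0.05 | One visit, k = 12 |
|---|---|---|---|---|
| Overall (324 per arm) | 1.2 to 2.1 | 1.6 to 2.8 | 1.8 to 3.1 | 2.3 to 4.1 |
| Within type (54 per arm) | 3.0 to 5.2 | 3.9 to 6.9 | 4.3 to 7.5 | 5.7 to 10.0 |

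**Power for the stated 1.2 points** (SD 8, four-visit mean). The standard error is 8 × 0.689 × √(2/324) = 0.433, and 1.2/0.433 = 2.770.
- Uncorrected: 2.770 − 1.960 = 0.810, which is 79%.
- k = 12: 2.770 − 2.865 = −0.095, which is 46%.

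**Sensitivity to k.** With k = 6 and the four-visit mean, the ranges are 1.5 to 2.6 overall and 3.7 to 6.5 within type. With 24 single-visit tests (12 sub-scales at two visits), they are 2.5 to 4.3 and 6.0 to 10.6.

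**The case against.** **Quality of life appears in both definitions,** so the sample-size text could be read as naming a subset. That is true, but with no secondary tier the other five families remain primary, so the conflict stands.

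**A reader might infer that the correction leaves the trial underpowered for quality of life.** The documents do not support this for the overall comparison. Even with 24 single-visit tests at SD 14, the detectable difference is 4.3 points, below both thresholds, and power for 5 points is 93%. Only the within-treatment-type comparison can fall short. There, at SD 14 and one visit, the figure is already 7.5 points before any correction.

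**A reader might infer an inflated false-positive rate,** for example 1 − 0.95^12 = 46% for 12 independent uncorrected tests. That is not the plan's error rate, because the plan commits to Bonferroni. The gap is that the family is undefined.

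**A reader might say that the plan ignores multiplicity in all its power work.** It does not: the separate calculation for utility profiles uses a Holm-adjusted alpha of 0.0125. The point is confined to the between-arm figures.

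**A reader might treat the missing PCI as the reason why power covers one family.** It is not. EPIC is the PCI's expanded edition, so this is a separate instrument mismatch. What remains is that the SD and meaningful-change figures are stated for PCI and have not been shown to hold for EPIC.

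**A reader might take six and 24 months as already fixed for the arm comparison.** That emphasis sits under Aim 4, which covers the intervention group only. Holm likewise appears only for the profile comparisons and Aim 4.

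**Conclusion.** The concern holds as a conflict over the primary outcome, together with a between-arm power statement that does not match the planned tests. With an assumed family of 12, correction alone multiplies the detectable difference by 3.707/2.802 = 1.32. Testing single visits instead of the four-visit mean multiplies it by a further 1/0.689 = 1.45. Using SD 14 in place of 8 multiplies it by 1.75.

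The practical effect differs by comparison. Overall, every recomputed value stays under 5 points, so no shortfall for quality of life is shown. Within treatment type, the corrected four-visit value reaches 6.9 points, above the lower end of the PCI range. The corrected single-visit value reaches 10.0, above both thresholds.

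These results assume a normal approximation, a plain two-group comparison without baseline adjustment, 10% loss in each arm, PCI-type SDs carried over to EPIC, and k = 12. Nothing can be computed for the other five families.

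**What to change.** 1. Reconcile the Primary outcome variable(s) field, the Secondary outcome variable(s) field and the sample-size text into one primary outcome for the Aim 3 between-arm comparison, and name it in Aim 3. Quality of life is the natural choice, being the only outcome in both definitions and the only one sized between arms. The other families would then be listed as secondary. That ranking is for the sponsor to settle. Treatment choice and regret, which the Aim 3 hypothesis names but neither primary definition includes, also need a place.
2. State the time points and the exact family of tests to which the correction applies. Use Holm in place of Bonferroni: it controls the same error rate and is never less powerful.
3. Replace PCI by EPIC in the sample-size text, and confirm that the SDs and meaningful-change values hold for EPIC.
4. Restate the detectable differences at the corrected alpha, over SD 8 to 14, and for the time points actually tested.

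The cost is a protocol and analysis-plan amendment and less favourable stated detectable differences. No extra patients or data are needed.
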